Title: Sibling-Support for Adolescent Girls (SSAGE): A study protocol for a pilot randomized-controlled trial of a whole-family, gender transformative approach to preventing mental illness among forcibly displaced adolescent girls

NCT number: NCT06078124

Date: July 12, 2024

Title:

Sibling-Support for Adolescent Girls (SSAGE): A study protocol for a pilot randomized-controlled trial of a whole-family, gender transformative approach to preventing mental illness among forcibly displaced adolescent girls

Principal Investigators:

[name], [contact]
[name], [contact]

Co-Principal Investigators:

[name], [contact]
[name], [contact]

Date and Version:

July 12, 2024 Version 1

Abstract

Forcibly displaced adolescents, especially girls, are at increased risks for mental illness and distress, with adolescent girls disproportionately affected in part due to the heightened gender inequity that often accompanies forced displacement. Although the family unit has the potential to prevent mental illness and promote healthy development in adolescents, few family interventions have employed a gender transformative approach or included male siblings in an effort to maximize benefits for adolescent girls.

This study will assess an innovative whole-family and gender transformative intervention—Sibling Support for Adolescent Girls in Emergencies (SSAGE)—to prevent mental health disorders among adolescent girls in Colombia who were recently and forcibly displaced from Venezuela. The study will employ a hybrid type 1 effectiveness-implementation pilot randomized control trial (RCT) to test the program's effectiveness and mechanistic pathways as well as to explore determinants of implementation in order to establish the feasibility, acceptability, and fidelity of SSAGE.

To address these aims, we will enroll 180 recently arrived, forcibly displaced adolescent girls in an RCT and examine the program's effectiveness on the prevention of mental illness (through reduction in anxiety, depression, interpersonal sensitivity, and somatization symptoms) one-month post-intervention. We will use contextually adapted and piloted measures to collect additional data on the hypothesized mechanistic pathways, including family attachment, gender equitable family functioning, self-esteem, and coping strategies. The implementation evaluation will employ mixed methods to assess the program's feasibility, acceptability, fidelity and barriers and facilitators to successful implementation. Potential findings can support humanitarian program implementation, as well as inform policy to support adolescent girls' mental health and to prevent the myriad disorders that can arise as a result of exposure to displacement, conflict, and inequitable gender norms in their households and communities.

Background and Rationale

Forcibly displaced children and adolescents face heightened levels of mental distress and illness (1–3). Evidence demonstrates that many experiences surrounding the forced migration process—such as exposure to conflict and violence, family loss or separation, and other adverse events—serve as risk factors for mental distress among displaced adolescents (2). Adolescent girls face additional gendered exposures in humanitarian settings, including intimate partner and non-partner physical and sexual violence, early marriage, and sexual exploitation, which may serve to exacerbate mental distress and health (2,4). Mental illness among forcibly displaced girls most often manifests through internalizing behaviors and symptoms, such as anxiety, depression, and psychosomatic symptomology (2,4,5).

The mental well-being of adolescent girls may be further impacted by gender inequitable attitudes and norms, which are often exacerbated in humanitarian settings (6–8). Previous research from low-income country and refugee settings reveals a strong relationship between gender inequitable norms at the community level and lowered self-esteem and well-being at the individual level for adolescent girls (7,9). Girls who internalize norms that marginalize and devalue their role within the family and community, may experience lowered self-esteem, perceived agency and resilience (7,10,11). Inequitable

To generate evidence on what works to prevent mental illness among forcibly displaced adolescent girls, Washington University in St. Louis, Universidad de Los Andes, Women's Refugee Commission, and Mercy Corps are conducting a hybrid type 1 effectiveness-implementation pilot randomized-controlled trial (RCT) of Sibling Support for Adolescent Girls in Emergencies (SSAGE). SSAGE is a whole-family and gender-transformative mental health intervention that aims to foster more secure family attachments, improve girls' self-esteem, and strengthen healthy coping skills on the path to improved mental health for forcibly displaced adolescent girls. The objectives of this hybrid type 1 pilot RCT are twofold. First, the study aims to examine the preliminary effectiveness and mechanistic pathways of SSAGE to prevent mental health disorders among recently arrived, forcibly displaced adolescent girls in Colombia; and second, the study seeks to assess the feasibility, acceptability and fidelity of the SSAGE intervention and identify determinants of successful implementation.

Study objective

- Primary Objective: The study aims to assess the effectiveness of the SSAGE intervention in preventing mental health disorders among recently displaced adolescent girls in Colombia, particularly focusing on reducing symptoms of anxiety, depression, interpersonal sensitivity, and somatization.

- Secondary Objective: The study seeks to explore the mechanistic pathways through which SSAGE operates, including its impact on family attachment, gender equitable family functioning, self-esteem, and coping strategies.
- Implementation Evaluation: Additionally, the study will evaluate the feasibility, acceptability, and fidelity of implementing SSAGE, including identifying barriers and facilitators to successful implementation at endline.

Methodology

We will undertake a hybrid type 1 effectiveness-implementation pilot RCT to test the effectiveness and mediators of SSAGE while simultaneously using a concurrent, convergent mixed methods design to examine the acceptability, feasibility, and fidelity of the intervention.

Screening for Eligibility: Inclusion Criteria

Recruitment for this study will draw from families who fled Venezuela and relocated to Colombia within the last year. Included among this population are families originally born in Colombia who had previously emigrated to Venezuela for at least five years and subsequently returned to Colombia. Eligibility requirements include adolescent girls aged 13-19 years old who: live with a male and female caregiver and an adolescent male sibling or relative; immigrated to Colombia within the last year; are available, along with their family members, to participate in the SSAGE intervention for three months; and are available to participate in survey questionnaires immediately before and one month after the intervention (please see Figure 1 for a study schedule). We will recruit 180 adolescent girls from 180 families. Study participants will be recruited by Mercy Corps and consented and enrolled in the study by Los Andes University.

Figure 1. Schedule of enrolment, interventions, and assessments

DATA ANALYSIS AND DISSEMINATION												
Analysis					X	X	X	X	X	X		
Write-up of findings									X	X	X	X
Dissemination											X	X

Subject Recruitment, enrollment, treatment assignment and sample size

Following confirmation of eligibility criteria, the study team will obtain informed parental consent and direct assent from potential adolescent girl participants. Every adolescent girl recruited to the study will be assigned a unique study identification number to enable tracking survey responses across points of data collection.

Sample size and power analysis: To detect a medium effect size in our primary outcomes of interest of $d=0.5$, assuming statistical power of 80% and a one-sided alpha of 0.05, we need a sample size of 63 adolescent girls in each study arm. We expect approximately 20% attrition from baseline to T2 either through: (1) declining to participate in subsequent rounds of data collection or (2) data collectors' inability to locate the participant. Additionally, when estimating the effect of SSAGE on the four outcomes of interest, we will exclude adolescent girls already exhibiting above-threshold scores on the four-dimension measure of mental health symptoms at baseline as it would not be possible to 'prevent' mental health disorders in this subgroup. We expect this to result in the loss of an additional 10% of the initial sample. As such, we require a sample size of 90 girls for each study arm.

Following the recruitment of 180 girls from 180 families, 90 adolescent girls each will be randomized to the treatment and control arm using a random number generator. Randomization will not be blinded.

Consent

Prior to data collection, participants and their caregivers (for those under 18 years of age) will be informed about the study's purpose, procedures, potential risks, and safeguards, including confidentiality and referrals for services. They'll learn that participation in the SSAGE intervention is random but not being selected won't affect access to future programs. Participation is voluntary, and participants won't face penalties for declining. They can withdraw at any time and refuse to answer questions. Participants will be informed about data usage. Researchers will ensure genuine informed consent by providing thorough explanations, multiple opportunities for questions, and avoiding coercion. Staff will be trained accordingly. The appendix contains the informed consent document that requires participant signature or parent/guardian signature for participants under the age of 18 years.

Data Collection

To measure effectiveness of the intervention, all 180 adolescent girls in the study (both treatment and control arms) will complete a survey questionnaire through an enumerator-facilitated interview using computer-assisted personal interview (CAPI) software immediately prior to the onset of the intervention. These same participants will be visited one month following the completion of the 12-week intervention (T2) to take the same survey using CAPI. The survey questionnaire is expected to take approximately 60 to 90 minutes to complete. Study participants' study identification will be used to link their survey responses between baseline and T2.

Study Outcome Measures and Ascertainment

The primary outcome measures include mental illness, anxiety and depression. A full list of primary and secondary outcomes, corresponding sources of measurement, and hypothesized directions of change can be found in Table 1. Relevant socio-demographic variables will also be collected, including age, education status, caregiver employment status, current living situation and household composition, relationship status, time in Colombia, country of birth, stressful life events, and other support services being received by the household. Survey tools will be translated into Spanish and back-translated.

Before each participant leaves the data collection site, their data will be reviewed by a data collector for completion. All data will be incrementally backed up each day on a secure data system and a full back-up will be performed weekly. The research team at Washington University in St. Louis will be responsible for weekly data checks to ensure data quality; errors will be reported to the local field team and rectified. Only selected, authorized WRC, Mercy Corps, University of Los Andes, and Washington University staff will have access to the password-protected data.

Table 1. Primary and secondary outcomes and hypothesized direction of change

Construct as presented in Figure 1	Source of measure	Hypothesized direction of change
Primary outcomes of interest		
Mental illness	DSM-V cross-cutting youth (35)	Decrease
Anxiety and depression	Revised Child Anxiety and Depression Scale-25 (36)	Decrease
Secondary outcomes/mediators		
Gender equitable family functioning	Gendered responsibilities scale (37)	Increase
Family attachment	Family Attachment and Changeability Index (FACI8) (38)	Increase

Improved self-esteem	Rosenberg Self-Esteem Scale (RSES) (39)	Increase
High instrumental coping skills	Kidcope (40)	Increase

Ethical Considerations:

Participants will be fully informed about the research study's ethical guidelines to ensure their rights and welfare are protected. Prior to data collection, participants will be asked to provide informed consent, ensuring they understand the purpose, procedures, risks, and benefits of participation. Furthermore, all research procedures will undergo review and approval by the Institutional Review Board to uphold ethical standards.

Risks and Benefits:

Participants will be informed about the potential risks involved in the study, such as discomfort or emotional unease when answering personal questions. However, participants will be assured that measures will be taken to minimize these risks, including the availability of support services if needed. While there may be no direct benefits to individual participants, they will be informed that their involvement could contribute valuable insights to benefit communities in humanitarian contexts, including Colombia, in the future.

Safety and Adverse Events:

To prioritize participant safety, support services will be readily accessible to participants through Mercy Corps and other local resources if they experience any adverse events or discomfort during participation. Confidentiality measures will also be implemented to protect participant privacy and ensure the security of personal information. Participants will be reassured of their right to withdraw from the study at any time without facing any negative consequences.

Data Analysis

Statistical methods

To assess the effectiveness of SSAGE in preventing mental health disorders, we will test the null hypothesis that adolescent girls who participate in SSAGE exhibit the same or greater levels of mental health symptoms as compared to girls who receive care as usual. We will test this hypothesis using both an intent-to-treat and per protocol analytical approach (41,42). We will employ generalized linear regression models to estimate the effect of the intervention on the primary outcomes, controlling for covariates not balanced between the two study arms at

baseline; given that treatment assignment is random, we expect that we will not need to control for many covariates. Per protocol analysis will also be conducted, leveraging attendance data from all participating family members. The threshold for meeting program adherence will be defined alongside program implementers prior to program implementation.

As a secondary, exploratory analysis, we will examine the effect of SSAGE on gender equitable family functioning, family attachment, self-esteem and coping strategies (see mechanistic pathways in Figure 1); and, we will assess if the effect of SSAGE on each of the primary outcomes of interest is mediated by these four secondary measures. The effect of SSAGE on each secondary outcome will be assessed using linear regression models (as described above). Mediation analysis will be conducted using structural equation modeling to estimate the degree to which each secondary measure mediates the impact of SSAGE on the prevention of mental health disorders. To avoid a reduction in statistical power and potentially biased results, we will employ iterative Monte Carlo Markov Chain (MCMC) multiple imputation to handle missing data in Stata. We will first generate 50-100 imputed datasets using expectation-maximization algorithm as estimates on which we will employ the MCMC procedure. All statistical inferences will then be made using the combined results across all complete datasets

Implementation evaluation

Qualitative implementation evaluation data—including key informant interviews with program staff and mentors (n=8) (43) and semi-structured in-depth interviews with a subset of individuals in the treatment arm (n=24)—will be conducted immediately following the end of the intervention to assess program acceptability, feasibility, and fidelity, and to identify implementation determinants (i.e., barriers and facilitators) that may influence the quality of program delivery.(44,45) Program participants will be purposively sampled in order to ensure representation from all cohorts (male caregivers, female caregivers, adolescent boys, and adolescent girls) as well as levels of adherence to the treatment protocol including number and length of sessions delivered as well as attendance. By also including participants with low attendance, we will be able to explore fidelity as well as potential barriers to acceptance and feasibility. Program mentors and staff will also be purposively sampled to ensure representation across target cohorts and levels of oversight, respectively, in order to inform an exploration of implementation determinants. Interview guides will be guided by the Exploration, Preparation, Implementation, and Sustainment (EPIS) Framework(46,47) and Implementation Outcomes Framework(48) and will focus on the facilitators of and barriers to program implementation as well as the acceptability, feasibility, and fidelity of SSAGE. Interviews will be recorded, translated, transcribed, and cleaned for analysis.

SSAGE's acceptability and feasibility will also be measured through administration of the acceptability and feasibility sub-scales of the Mental Health Implementation Science Tools (mhIST). These two scales will be administered to all treatment participants (n=90) at T2, as part

of the quantitative survey.(49) The mhIST was developed specifically for use in low-resource settings and the tool has been validated in multiple low- and middle-income countries, including in Colombia.(49) Each scale includes 15 questions that are answered by the respondent using a Likert scale.

Descriptive statistics for the mhIST items and scales will first be estimated to identify perceptions of program acceptability and feasibility. Qualitative data will be imported into a qualitative data analysis software and analyzed using qualitative content analysis, a theory-driven approach that will involve both deductive and inductive coding.(50,51) Deductive codes will be derived from guiding conceptual frameworks.(46,48,52) Mixed methods analyses will involve merging the quantitative and qualitative data in joint displays to examine the extent to which the two types of data converge. These results will inform further refinements of SSAGE and the identification of implementation strategies that may be needed to address identified determinants and ensure that the intervention is routinely delivered with high quality.

Data Handling, Confidentiality and Security

U.S. government representatives, including the Office for Human Research Protections, may access records pertaining to this research to fulfill federal or state responsibilities. Representatives from the National Institute of Mental Health, the University, and the Institutional Review Board (IRB) oversee the conduct of this study. All identifiers will be removed from data, which will be stored in a separate locked file cabinet. Once entered into computer files, data will be password protected, with access restricted to the research team. Data shared with others will be stripped of identifiers and coded for anonymity. This research is covered by a Certificate of Confidentiality from the federal U.S. government, allowing researchers to refuse to disclose information that may identify participants in legal proceedings or to unauthorized individuals. Participants have the right to control the disclosure of their information and involvement in the study, including granting permission for the research team to disclose their information to third parties.

References

1. Bryk, A. S., & Raudenbush, S. W. (1992). Hierarchical linear models: Applications and data analysis methods. Sage Publications, Inc.
2. Fitzmaurice, G. M., Laird, N. M., & James, H. (2004). Ware. 2004. Applied longitudinal analysis, 3462-3469

3. Goldstein, H. (1995). Hierarchical data modeling in the social sciences. *Journal of Educational and Behavioral Statistics*, 20(2), 201-204.
4. Kabeer, N. (1999). Resources, agency, achievements: Reflections on the measurement of women's empowerment. *Development and change*, 30(3), 435-464.

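### The 63 girls per arm do not follow from the stated one-sided alpha of 0.05: that needs 50 to 51, and 63 is the two-sided 0.05 figure

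*Protocol*

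**What the plan says.** The protocol's paragraph on sample size and power sets a medium effect of d = 0.5 on the primary outcomes and continues: "assuming statistical power of 80% and a one-sided alpha of 0.05, we need a sample size of 63 adolescent girls in each study arm". It then allows for about 20% attrition to T2, and for a further 10% of the initial sample excluded for above-threshold symptoms at baseline. It concludes: "As such, we require a sample size of 90 girls for each study arm". The next paragraph randomises 90 girls to each arm, 180 in all.

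Under Statistical methods the protocol states a directional null hypothesis, that girls who take part in SSAGE "exhibit the same or greater levels of mental health symptoms as compared to girls who receive care as usual". Table 1 gives a hypothesised direction of change for every outcome.

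The SAP has no sample size section and states no significance level, sidedness or confidence level. Its sections 5.1 and 5.2 plan OLS and two-stage least squares models in Stata.

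**The concern.** All the inputs to a standard two-group calculation are given, so the 63 can be checked, and it looked too large for a one-sided 5% test. It is the familiar answer for a two-sided 5% test at d = 0.5.

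Two things are at stake. First, the number that sizes the trial is not supported by the assumptions offered for it, so the stated power or the stated alpha is wrong. Second, the rule for declaring an effect is unclear. The wording of the alpha and the null point to a one-sided 0.05 test, the sample size points to a two-sided one, and the SAP does not settle it. Regression output usually shows two-sided p-values, so an analyst working from the SAP alone could well use those. A one-sided p-value between 0.025 and 0.05 in favour of SSAGE would then be positive under one rule and not under the other, and the choice could be made after the result is known.

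**Working it through.** **Inputs (protocol, sample size and randomisation paragraphs).** d = 0.5, so the SD is 1 by definition; power 80%; alpha 0.05, stated as one-sided; allocation 1:1; stated requirement 63 per arm; losses 20% + 10% = 30% of those enrolled; stated enrolment 90 per arm.

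**Formula (normal approximation).** n per arm = 2 × (z_alpha + z_power)² / d², with z_power = 0.842 and 2/0.5² = 8.

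| Test | z_alpha | n per arm, normal | n per arm, t-test |
|---|---|---|---|
| One-sided 0.05 (as stated) | 1.645 | 8 × (2.486)² = 49.46, so 50 | 50.15, so 51 |
| Two-sided 0.05 | 1.960 | 8 × (2.802)² = 62.79, so 63 | 63.77, so 64 |

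The stated 63 is reproduced only by the two-sided row, under the normal approximation. It exceeds the one-sided requirement by 12 to 13 girls per arm.

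**Inflation for losses.** 63 / (1 − 0.30) = 90.0, exactly the stated enrolment. So 63 is the number before losses, and the inflation step is correct. Under the one-sided assumptions as written, the same step gives 50/0.70 = 71.4, so 72 per arm (144 girls), or 51/0.70 = 72.9, so 73 per arm (146 girls). Against 180, the difference is 36 or 34 families.

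**Power with 63 analysed per arm.** Normal approximation: power = Φ(d × √(n/2) − z_alpha), and 0.5 × √31.5 = 2.806.

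| Test | Normal | t-test | d detectable at 80% power (t-test) |
|---|---|---|---|
| One-sided 0.05 | Φ(1.161) = 87.7% | 87.4% | 0.445 |
| Two-sided 0.05 | Φ(0.846) = 80.1% | 79.5% | 0.503 |

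**Other routes to 63.**
- One-sided 0.05 split equally over two primary outcomes (0.025 each) also gives 63. Table 1 lists two primary outcomes, but neither document mentions a split. A split over the four outcomes named in the sample size paragraph would need 77 to 78.
- 50/0.80 = 62.5, so 63 could be 50 already inflated for 20% attrition. The text introduces attrition only after giving 63, and 63/0.70 is exactly 90. On this route attrition would have been counted twice.
- One-sided 0.05 gives 63 at about 87.5% power, which is not the power stated.
- No design effect is given, and there is one girl per family.

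**The case against.** The strongest reply is that the error does no harm to the trial's size. The protocol asks for more girls than its stated assumptions require, and enrolment would not change. That is correct, and it limits the weight of the point.

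A second reply is that the protocol is consistently directional in its alpha, its null hypothesis and Table 1. On this view the smaller repair is to correct the power and keep the one-sided test. This also stands as a legitimate choice. Moving to two-sided testing changes the rejection rule and is more than an edit to one number. It also follows that testing at one-sided 0.05 would not exceed the declared error rate. It would be twice the 0.025 that yields 63, but that smaller level is inferred and is stated nowhere.

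Third, the SAP's silence is an omission, not a contradiction, and the protocol's alpha could be read as governing. That is fair, but the protocol's alpha and its sample size disagree with each other, so relying on the protocol does not settle which was meant.

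Fourth, the power figures assume an unadjusted comparison of a continuous outcome with 63 analysed per arm. The SAP turns one primary outcome into 12 dichotomous variables, plans baseline-adjusted models, and does not repeat the 10% baseline exclusion. Without that exclusion, 20% attrition leaves 90 × 0.80 = 72 per arm, with t-test power of 91.0% one-sided or 84.6% two-sided. These points limit how far the figures describe the final analysis. They do not reconcile the stated alpha, power and 63.

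**Conclusion.** The concern holds. With d = 0.5, 80% power and 1:1 allocation, one-sided 0.05 requires 50 to 51 girls per arm. The stated 63 is the normal-approximation figure for two-sided 0.05. At 63 per arm the t-test power is 87.4% under the stated test and 79.5% under the two-sided one. The mismatch is certain. Its origin is an inference: a two-sided calculation described as one-sided is the likeliest explanation, because it gives 63 directly and 63/0.70 is exactly 90.

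The direction is conservative, and 180 girls suffice on either reading, or fall at most two per arm short by the t-test (64/0.70 = 91.4, so 92). The practical consequence is the unsettled significance rule, which should be fixed before outcome data are analysed. The figures rest on a two-group comparison of a continuous outcome with no multiplicity adjustment or design effect, since the documents give none.

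**What to change.** Choose one rule and state it in the protocol's sample size paragraph, in its Statistical methods section and in the SAP.

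- **Two-sided:** change the alpha to two-sided 0.05 (about 80% power with 63 analysable girls per arm), restate the null as no difference, and specify two-sided 0.05 with 95% confidence intervals in the SAP. The price is a stricter threshold for benefit than the one-sided 0.05 now written. This keeps the 63, the 80% and the 90 as they stand.
- **One-sided:** keep one-sided 0.05 and the directional null, restate the power as about 87% at 63 per arm (or the requirement as 50 to 51 at 80%), and write the one-sided test and its level into the SAP.

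If 63 came from another route, such as a split of alpha over two primary outcomes, state that calculation in the protocol and the split in the SAP. Enrolment stays at 180 in every case. The changes are to text only, with no cost in recruitment or data collection.

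### Mediators and symptoms share a single post-baseline interview, so the exploratory SEM cannot separate mediation from reverse causation or shared causes, and the plan states no safeguard.

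*Protocol*

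**What the plan says.** Under Data Collection, the protocol has all girls surveyed "immediately prior to the onset of the intervention" and again "one month following the completion of the 12-week intervention (T2) to take the same survey using CAPI". The eligibility text agrees: girls must be "available to participate in survey questionnaires immediately before and one month after the intervention". No survey falls in between.

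Table 1 lists four scales as "Secondary outcomes/mediators" below the primary outcomes. They cover self-esteem, coping, family attachment and gender-equitable family functioning, and they belong to the same questionnaire as the symptom measures.

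Under Statistical methods, "Mediation analysis will be conducted using structural equation modeling", with the aim to "estimate the degree to which each secondary measure mediates the impact of SSAGE on the prevention of mental health disorders". The protocol labels this work secondary and exploratory. It does not say which baseline values enter the model, what assumption orders mediator and outcome, or how sensitive the result is to that assumption.

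The SAP describes no mediation analysis. Its Study Sample section places endline directly after the programme, not a month later. That needs reconciling separately, but it is still one post-baseline wave.

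**The concern.** Mediation needs two links: the arm changes the scale, and the change in the scale changes symptoms. Randomisation secures the first link but not the second. When scale and symptoms come from one interview, their association at T2 also contains any effect of symptoms on the scale (a girl who feels better may rate herself and her family more favourably) and any cause common to both. Recall windows do not help: SAP sections 2a and 2b give the DSM-V measure and KidCOPE the same two-week window.

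Mechanism is the protocol's secondary objective, and the abstract says the trial is designed "to test the program's effectiveness and mechanistic pathways". A quantified share of mediation could therefore be read as evidence for why SSAGE works, and could steer refinement of the programme, when the schedule cannot support that reading.

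**Working it through.** The documents give no figure for the mediation analysis, so there is none to reproduce. From the protocol's sample size section I take d = 0.5 and 63 evaluable girls per arm (126 in total). All correlations and path sizes below are assumptions. Write a for the effect of arm on the scale and b for the scale-symptom slope given arm. The mediated share is a × b divided by the total effect. True mediation is zero in steps 1 to 4.

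**1. Reverse causation, no baseline terms.** Let Y = 0.5X + e and M = rY + √(1 − r²)u, with unit residual variances (both scored in the same direction).
- a = 0.5r and b = r, so the share is 0.5r² / 0.5 = r².
- r = 0.4, 0.5, 0.6, 0.7 gives 16%, 25%, 36%, 49%.

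**2. Reverse causation, adjusted for baseline mediator and outcome.** Assume a baseline correlation of −0.4, Y = −0.5X + 0.5Y₀ + e₁ and M = −cY + 0.3M₀ + e₂, with both residual variances 0.75.
- In absolute value, a = 0.5c and b = 0.75c / (0.75c² + 0.75) = c / (1 + c²), so the share is c² / (1 + c²).
- c = 0.2, 0.3, 0.5, 0.7 gives 4%, 8%, 20%, 33%.
- In 4,000 simulated trials of 126 girls, both paths were nominally significant in about 6%, 14%, 30% and 44%. At 20,000 girls the shares were unchanged, so this is bias and not a small-sample effect.

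Steps 1 and 2 are different scenarios, not a before-and-after pair. Without baseline terms, the step 2 model gives c(c + 0.06) / (c² + 0.12c + 0.84), which is 6%, 11%, 24% and 38%. In that scenario adjustment helps only a little.

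**3. Shared cause arising after baseline.** SSAGE moves scale and symptoms separately by 0.5. An unmeasured cause with variance 0.36 acts on both, and each remaining residual variance is 0.75² × 0.75 = 0.42. After baseline adjustment the share is 0.36 / (0.36 + 0.42) = 46%. Both paths were significant in 88% of simulated trials of 126 girls.

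**4. Stable shared trait.** SSAGE again moves both separately by 0.5. The trait explains a fraction λ of each unit-variance score at both waves. Unadjusted, the share is λ. Adjusted, it is λ / (1 + 2λ). For λ = 0.5 it falls from 50% to 0.5 / 2 = 25%. For λ = 0.7 it falls from 70% to 0.7 / 2.4 = 29%. Here the baseline terms do real work.

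**5. Scale correlated with symptoms but not moved by the arm.** Then a = 0 and a × b = 0. Simulation with 63 per arm and r from 0.4 to 0.7 gave a mean share of 0%, with both paths significant in about 5% of runs.

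**6. Can model fit choose the order?** No. The arm-scale-symptom and arm-symptom-scale models, each with baseline terms, had the same maximised log-likelihood in every simulated dataset (differences below 1e-10).

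**The case against.** The strongest reply is that the protocol already hedges. It calls the analysis exploratory and the trial a pilot, and one follow-up wave is a common limit of a small study. This stands as to weight: the point concerns the mechanistic claim only. But an exploratory label does not make a numerical share of mediation interpretable.

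A reader might infer that every self-report scale correlated with symptoms will appear as a mediator. That does not follow. Step 5 shows that the arm must also move the scale, and the trial can test that under randomisation. Nor need mood drive all four scales alike: nothing in the documents shows that reports of household task sharing follow symptoms as self-esteem might.

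The r-squared range is one unadjusted, linear scenario. The SAP treats the DSM-V measure as 12 dichotomous domains and examines coping strategies one by one, so the formula does not carry over directly to those variables. The protocol also does not write out the SEM paths, and the SAP's treatment models do include baseline control, so baseline terms may be intended. They are not stated for mediation, and they would not settle direction.

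Excluding girls above threshold at baseline narrows the room for symptom relief, but does not order the two measurements.

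Finally, a reader might infer that the later SAP dropped mediation. Its silence fits either dropping it or leaving it unspecified, and the documents do not say which.

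**Conclusion.** The concern holds for the exploratory mediation analysis. With one post-baseline interview, the scale-symptom path rests on assumption, and the plan states neither an assumption nor a check. Where SSAGE moves a scale, directly or through symptoms, a false mediated share can follow: 16% to 49% in the simple unadjusted scenario, about 4% to 33% with baseline adjustment in the second, and 46% with a shared cause arising after baseline. These sizes depend on assumed values. The lack of identification does not.

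It would go too far to say that the mediation work has no value or that the trial's main result is compromised. The effects of SSAGE on each scale and on symptoms remain protected by randomisation, and the primary intent-to-treat estimate is unaffected. Nor is the path beyond any identification: strong, explicitly stated restrictions might identify it, but the plan offers none. The change is worth making because it is cheap and keeps the mechanistic claim within what the schedule supports.

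**What to change.** In the mediation text of the protocol's Statistical methods section:

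- Enter the baseline mediator and the baseline outcome in every SEM equation. This reduces stable between-girl confounding. State that it does not settle direction.
- Add a sensitivity analysis showing how large a residual mediator-outcome correlation would bring each indirect effect to zero.
- Report the reverse-order model beside each mediator model only to display the ambiguity. It cannot serve as a pass-or-fail test, because the two orders fit equally well.
- Replace the promise to "estimate the degree to which each secondary measure mediates the impact of SSAGE on the prevention of mental health disorders" with an aim to describe a *concurrent association consistent with mediation*.

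If the mediation analysis is kept, put the same text in the SAP. If it is not, say so there.

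The cost is wording and a few extra models on variables already in the survey. It needs no new visit and no change to the primary analysis. The downside is a weaker mechanistic claim.
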